#### **Analysis of the lymphocyte subpopulations in peripheral blood by flow cytometry:**

Determinations were done with the same periodicity as for the DSA. Blood samples anticoagulated with EDTA (10 ml) were obtained. A volume of 50 ml was incubated in Falcon polypropylene tubes 12 x 75 mm within 48 hours of extraction with the following monoclonal antibodies: CD4, CD127, CD25, CD183 and CD194 labeled with the fluorochromes FITC, PE, APC, APC-Cy7 and Per-CP. In the window for the CD4+ lymphocytes we studied the expression for the markers CD183 and CD194 and in the window for the CD4 +CD25high CD127 lymphocytes we studied the expression of CD183 and CD194 in the Treg cells. The acquisition and analysis was done in at least 5000 lymphocyte cells with a FACScanto II dual-laser cytometer with FACSdiva software. Each sample of the aspiration cytology underwent the same analysis in a sample of blood anticoagulated with EDTA (3ml) for the comparative analysis.

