## **STUDY PROTOCOL.**

### **HYPOTHESIS**

Steroids form one of the pillars of immunosuppression in transplant patients. However, their use is associated with an increase in post-transplant comorbidity. Although steroid withdrawal post-transplant can improve the metabolic and cardiovascular profile in transplant patients, it is not really known whether this therapeutic strategy results in a greater risk for the de novo appearance of donor-specific antibodies (DSA), which are associated with a reduction in kidney graft survival. Also unknown is the causal relationship between the appearance of DSA and histological lesions in stable kidney transplant patients after steroid withdrawal in the third post-transplant month. Finally, another unknown is whether this immunosuppressive strategy is associated with changes in the balance between effector and suppressor lymphocyte subpopulations that selectively infiltrate the graft via peripheral homing receptors.

This randomized controlled study of stable kidney transplant patients aimed to determine the natural history after steroid withdrawal in the third month post-transplant of the de novo production of anti-HLA antibodies (DSA), by means of the sequential measurement of DSA during the first two years post-transplant. At the same time we wished to determine the repercussion of this therapeutic strategy on the kidney graft histology by performing protocol biopsies, as well as the risk factors for the appearance of de novo DSA in these patients. Finally, we aimed to monitor sequentially the balance of the lymphocyte (CXCR3highCD4+/CCR4highCD4+) and regulatory cell (Treg CCR4high) subpopulations in peripheral blood and samples of the graft tissue obtained by fine-needle aspiration puncture (FNAP) after the withdrawal of steroids versus continuation of conventional triple therapy.

The lack of prospective serological, histological and lymphocyte subset studies in kidney transplant patients in whom steroids are withdrawn makes this study very pertinent. The findings will doubtless give rise to an immunosuppressive strategy that optimizes the results of a transplant in terms of survival.

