### *Secondary objectives*

1. To determine the course of the histological findings in the two treatment groups.
2. To determine the course of the balance in the subpopulations of lymphocytes (CXCR3highCD4+/CCR4highCD4+) and regulatory cells (Treg CCR4high) using flow cytometry in samples from peripheral blood and FNAP after withdrawal of steroids in the third month post-transplant versus conventional triple immunosuppression.
3. To analyze and compare the incidence of immunological dysfunction in the two treatment arms, as well as graft and patient survival at one and two years of follow-up.
4. To examine the potential metabolic and cardiovascular benefit of steroid withdrawal in terms of renal function, hypertension, diabetes and hyperlipidemia.
5. To assess the adherence to treatment with immunosuppressors in the two treatment groups and its impact on the generation of DSA.

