### **Variables:**

#### *Efficacy variables:*

The *primary variable* was the presence of donor-specific anti-HLA antibodies (DSA) at 24 months.

The *secondary variables* were:

- a) Graft and patient survival.
- b) Rate of acute clinical rejection, confirmed by biopsy, calculated glomerular filtration rate (determined by aMDRD) and proteinuria at 3, 6, 12 and 24 months.
- c) BP figures and number of hypertensive patients, lipid levels and need for lipid-lowering drugs, and increase in weight and BMI.
- d) Rate of post-transplant diabetes mellitus (PTDM) or glucose intolerance one year post-transplant according to the criteria of the ADA (PTDM: baseline glycemia  $\geq 126$ , or  $\geq 200$  mg/dl after glucose overload, or need for treatment; glucose intolerance: glycemia after overload of 140-199 mg/dL).
- e) Determination of the lymphocyte subpopulations (CXCR3highCD4+; CCR4highCD4+ and Treg CCR4high) by flow cytometry at 1, 3, 6, 12, 18 and 24 months.
- f) Appearance of acute or chronic pathological lesions of the graft using:

\*Kidney graft biopsy. Biopsies were done before randomization (month 3 post-transplant) and in month 24 post-randomization (protocol biopsies). In the case of suspected acute rejection a biopsy of the graft was done before or within 48 hours of starting anti-rejection treatment. Likewise, a graft biopsy was done at any time if graft dysfunction was detected, as evidenced by proteinuria 0.5 g/day or an increase in the serum creatinine of 25% above its baseline level. The biopsies were evaluated according to the Banff'09 classification (*Sis B, et al Am J Transplant 2010;10: 464-71*). Biopsies done for clinical indication and those done prior to randomization were evaluated locally at each participating center. The local pathologist interpreted the biopsy for the presence of clinical or subclinical rejection, borderline lesions or progression of chronic lesions that

explained a possible graft failure to thus provide the most opportune treatment. The biopsies done and the pre-randomization and final visits were also sent to the pathologist at Carlos Haya Hospital, Malaga, who also interpreted and classified them using the same Banff'09 criteria. The biopsies were processed in each center and sent to the central pathologist for study. The slides comprised at least 2-3 slices of the biopsy. The staining was done locally (hematoxylin eosin, periodic acid Schiff, Masson trichrome and methenamine silver).

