#### **FNAP for morphological analysis and flow cytometry:**

The FNAP was done according to the technique of Hayry (Kidney Int. 1989;36:130-141) with the same periodicity as that for the DSA and if there was any suspicion of immune dysfunction. Aspirate samples were obtained with a Ham solution (10 ml). With the 0.8 mm / 25G needle implanted in a Cameco-Gun device the cortical region of the graft was punctured with local anesthesia, and aspirating by vacuum about 20  $\mu$ L of cell material in a Hepes buffer culture

medium with heparin and human serum albumin (Ham solution). At the same time, a blood sample was obtained to calculate the corrected index (CI), which was the result of the differential in the leukocyte count between the FNAP specimen and the peripheral blood sample. The numerical differences for each cell subtype were multiplied by a correction factor and the sum of the different corrected increases described the intensity of the inflammation. A CI greater than 3 was considered suggestive of acute rejection. The aspirate was processed by flow cytometry to analyze the lymphocyte subpopulations in the same way as these were analyzed in peripheral blood, described above.

**Other determinations:** The patients were monitored for renal function, levels of calcineurin inhibitors, blood count and other parameters, and imaging tests as per clinical practice in Spain. The concomitant treatment was also as usual. The fasting glucose figures were monitored daily during the first week, at least twice during the second week, and at least weekly until the end of the first month. During the second and third months they were monitored at least once every two weeks. With effect from the third month and until the end of the first year they were monitored at least once a month. The HbA1c was measured and a standard oral glucose tolerance test of 75 gr was done at 3, 12 and 24 months.

**Pregnancy tests:** These tests were done for all women who were potentially considered to be of child-bearing age in phases I (screening) and II (randomization) of the study. The pregnancy tests were done locally in serum using detection of the human chorionic gonadotropin hormone.

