## **STATISTICAL ANALYSIS PLAN.**

Descriptive statistics are presented together with the various analyses. Both an intention-to-treat analysis and an analysis according to the final treatment were done. The categorical variables were analyzed using the chi-square test or Fisher's exact test, according to needs. The quantitative data were analyzed using the Student t test or the Mann-Whitney U test, according to needs. Changes over time in the DSA and lymphocyte subsets in the two study groups were analyzed using a general linear model for repeated measures, adjusting for confounding variables. Correlations between the various subsets were analyzed using Pearson correlation. The graft and patient survival curves were calculated with the Kaplan-Meier method. The rates of survival of the groups were compared with the log-rank test. Finally, a linear regression analysis was done to determine the factors associated with the generation of de novo DSA, including steroid withdrawal. The data were analyzed using SPSS 20.0.

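### As documented, the CCR4high and CXCR3high CD4+ subsets include the regulatory cells, so their correlation with Treg CCR4high is partly built in and a change in them cannot be assigned to non-regulatory cells

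*Combined protocol and SAP*

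**What the plan says.** The Hypothesis section asks whether steroid withdrawal is associated with "changes in the balance between effector and suppressor lymphocyte subpopulations". It names the populations to be followed as "the balance of the lymphocyte (CXCR3highCD4+/CCR4highCD4+) and regulatory cell (Treg CCR4high) subpopulations in peripheral blood" and in graft aspirates. Secondary objective 2 repeats the same three populations. Secondary variable (e) lists them one by one: "Determination of the lymphocyte subpopulations (CXCR3highCD4+; CCR4highCD4+ and Treg CCR4high) by flow cytometry".

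The flow cytometry section describes two readings. The first is "In the window for the CD4+ lymphocytes we studied the expression for the markers CD183 and CD194". The second is "in the window for the CD4 +CD25high CD127 lymphocytes we studied the expression of CD183 and CD194 in the Treg cells". The section on fine-needle aspiration carries this over to the graft: "The aspirate was processed by flow cytometry to analyze the lymphocyte subpopulations in the same way as these were analyzed in peripheral blood".

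The Statistical Analysis Plan models the change in the subsets by arm with a general linear model for repeated measures. It then adds: "Correlations between the various subsets were analyzed using Pearson correlation".

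Three things are not stated: whether Tregs are taken out of the CD4+ window, on what denominator each subset is expressed, and how the balance is calculated.

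**The concern.** A Treg is itself a CD4+ cell. If both markers are read on all CD4+ cells, each Treg that is CCR4high is counted twice, once in CCR4highCD4+ and once in Treg CCR4high. In the same way, each CXCR3high Treg is also counted in CXCR3highCD4+.

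Two things follow. First, correlating CCR4highCD4+ with Treg CCR4high correlates a whole with one of its parts. A positive coefficient could be taken as a biological link between two cell types when some or all of it is shared cells. If the real link were negative, the overlap could hide it.

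Second, a movement in Tregs alone moves CCR4highCD4+ and any ratio that contains it. The trial asks about effector against suppressor cells, and these variables do not separate regulatory from non-regulatory cells. The 3-month CCR4highCD4+ result reported under Lymphocyte subpopulations (inverse correlation with 24-month interstitial and tubular inflammation, r = -0.431 and -0.436) has this limit: it cannot be credited to regulatory or to non-regulatory cells.

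**Working it through.** **Step 1: are the subsets nested?** CD183 and CD194 are taken here to be CXCR3 and CCR4. The documents do not state this, but it is the evident meaning of the panel.

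| Subset | Window | Marker |
|---|---|---|
| CCR4highCD4+ (W) | CD4+ | CD194 |
| Treg CCR4high (T) | CD4+ and CD25high CD127 | CD194 |

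The second window adds conditions to the first, so T lies inside W. Write W = T + R, where R is the CCR4high cells outside the Treg window. The same holds for CD183, and for the aspirate.

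**Step 2: the correlation that the overlap creates.** Express T and W as percentages of CD4+ cells, and let T and R be independent, so that the true association is zero. Then r(T,W) = sd(T) / √(sd(T)² + sd(R)²). With equal coefficients of variation this reduces to T / √(T² + R²), using the means. The documents give no subset frequencies, so the means below are assumptions.

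| T, % of CD4+ | R, % of CD4+ | Treg share T/(T+R) | r(T,W) |
|---|---|---|---|
| 1 | 20 | 1/21 = 5% | 1/√401 = 0.05 |
| 3 | 12 | 3/15 = 20% | 3/√153 = 0.24 |
| 5 | 8 | 5/13 = 38% | 5/√89 = 0.53 |

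If Tregs vary relatively twice as much as the rest, T is replaced by 2T in the last column. At the 20% share, r becomes 6/√(36 + 144) = 0.45. With R in place of W, the built-in correlation is zero.

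**Step 3: against what threshold?** The two-sided 5% critical value is t / √(t² + n − 2).

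- n = 105 (all randomized): 1.983 / √(1.983² + 103) = 0.19.
- n = 38: 2.028 / √(2.028² + 36) = 0.32.

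The smaller number is inferred from the reported results. For r = −0.431 and n = 38, |t| = 0.431 × √36 / √(1 − 0.431²) = 2.87, which gives P = 0.007 as reported. For r = −0.436 the same P corresponds to n = 37. Those pairs needed 24-month histology, so a subset-to-subset correlation may have had more patients. The documents do not give that number.

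The Treg share at which the overlap alone reaches the threshold solves T/R = r/√(1 − r²). For r = 0.19 this is about 0.20, a share of 0.20/1.20, or about 16%. For r = 0.32 it is about 0.34, a share of 0.34/1.34, or about 25%.

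**Step 4: effect on a CXCR3high/CCR4high ratio.** Take the middle row (T = 3, R = 12) and double the Tregs only. CCR4highCD4+ goes from 15 to 18, up 20%. If no Treg is CXCR3high, the ratio is multiplied by 15/18 = 0.83, a fall of 17% with no change outside the Tregs. If CXCR3highCD4+ is an illustrative 12 plus x from Tregs, the factor is [(12 + 2x)/18] / [(12 + x)/15]. For x = 0, 1, 2 and 3 the fall is 17%, 10%, 5% and 0%. So 17% is the largest fall within this illustration.

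**The case against.** The best defence is that the plan does not make the comparison a critic would attack. A reader might infer that CCR4highCD4+ is set against Treg CCR4high, so that the balance partly compares a population with itself. The documents do not establish that. The slash in secondary objective 2 stands between the two CD4+ subsets, with the Tregs named beside them, and secondary variable (e) lists three separate measurements. No section defines an index. Nor does any section call CCR4highCD4+ an effector subset, so it cannot be said that the plan would read a Treg change as an effector shift. These points stand.

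It also stands that the randomized comparison of each subset is valid. The overlap changes what a subset means, not whether the arms can be compared on it. Treg CCR4high is measured in its own right, so a reader could see whether Tregs moved too.

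The size is open. At a 5% share the built-in correlation is negligible, and the 20% case (0.24) would not reach significance in 38 patients. The correlations in Step 2 need a common CD4+ denominator. If Treg CCR4high is a percentage of Tregs, they do not carry over. The reported results contain no correlation of one subset with another. An unwritten laboratory exclusion of Tregs is possible.

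These points limit the concern but do not remove it. Read as written, the two windows are nested, and the plan provides for correlating the subsets without excluding this pair. If an exclusion was applied, the flow cytometry section should say so.

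**Conclusion.** The point holds in a limited form. As documented, in blood and in aspirate, CCR4highCD4+ and CXCR3highCD4+ include the corresponding Tregs. On a common CD4+ denominator, the Pearson correlation of CCR4highCD4+ with Treg CCR4high is therefore partly positive by construction. The built-in part is about 0.05 to 0.5 for assumed Treg shares of 5% to 38%, given equal coefficients of variation and no true association. Whether that would pass for a finding depends on the share and on the number of patients, and the documents give neither for this correlation.

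A change in CCR4highCD4+, or in a ratio built on it, cannot be assigned to regulatory or non-regulatory cells. This limits the answer to the effector-versus-suppressor question. It bears on one mechanistic secondary variable and leaves the primary DSA variable untouched.

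**What to change.** In secondary variable (e) and in the flow cytometry section, define CXCR3high and CCR4high within CD4+ cells outside the CD25high CD127 window. Express these subsets and Treg CCR4high on a common CD4+ denominator. They can be obtained by subtracting the Treg counts from the CD4+ counts of the same sample, or by re-analysing the cytometry files if these were kept. Subtraction requires that the counts, or percentages that convert to counts, are available.

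In the Statistical Analysis Plan, use the non-overlapping subsets for the correlations between subsets and for any balance measure. State how the balance is calculated. Keep the whole-CD4+ subsets as a sensitivity analysis.

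No new sample, antibody or visit is needed if the counts or files exist. The cost is some laboratory analysis time and fewer events in each CD4+ subset.

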#### **FNAP for morphological analysis and flow cytometry:**

The FNAP was done according to the technique of Hayry (Kidney Int. 1989;36:130-141) with the same periodicity as that for the DSA and if there was any suspicion of immune dysfunction. Aspirate samples were obtained with a Ham solution (10 ml). With the 0.8 mm / 25G needle implanted in a Cameco-Gun device the cortical region of the graft was punctured with local anesthesia, and aspirating by vacuum about 20  $\mu$ L of cell material in a Hepes buffer culture

medium with heparin and human serum albumin (Ham solution). At the same time, a blood sample was obtained to calculate the corrected index (CI), which was the result of the differential in the leukocyte count between the FNAP specimen and the peripheral blood sample. The numerical differences for each cell subtype were multiplied by a correction factor and the sum of the different corrected increases described the intensity of the inflammation. A CI greater than 3 was considered suggestive of acute rejection. The aspirate was processed by flow cytometry to analyze the lymphocyte subpopulations in the same way as these were analyzed in peripheral blood, described above.

**Other determinations:** The patients were monitored for renal function, levels of calcineurin inhibitors, blood count and other parameters, and imaging tests as per clinical practice in Spain. The concomitant treatment was also as usual. The fasting glucose figures were monitored daily during the first week, at least twice during the second week, and at least weekly until the end of the first month. During the second and third months they were monitored at least once every two weeks. With effect from the third month and until the end of the first year they were monitored at least once a month. The HbA1c was measured and a standard oral glucose tolerance test of 75 gr was done at 3, 12 and 24 months.

**Pregnancy tests:** These tests were done for all women who were potentially considered to be of child-bearing age in phases I (screening) and II (randomization) of the study. The pregnancy tests were done locally in serum using detection of the human chorionic gonadotropin hormone.

## **STATISTICAL ANALYSIS PLAN.**

Descriptive statistics are presented together with the various analyses. Both an intention-to-treat analysis and an analysis according to the final treatment were done. The categorical variables were analyzed using the chi-square test or Fisher's exact test, according to needs. The quantitative data were analyzed using the Student t test or the Mann-Whitney U test, according to needs. Changes over time in the DSA and lymphocyte subsets in the two study groups were analyzed using a general linear model for repeated measures, adjusting for confounding variables. Correlations between the various subsets were analyzed using Pearson correlation. The graft and patient survival curves were calculated with the Kaplan-Meier method. The rates of survival of the groups were compared with the log-rank test. Finally, a linear regression analysis was done to determine the factors associated with the generation of de novo DSA, including steroid withdrawal. The data were analyzed using SPSS 20.0.

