## OBJECTIVES

### *Primary objective*

To compare the incidence of de novo DSA in stable kidney transplant patients after withdrawal of steroids in the third month post-transplant as compared with patients who continue to receive conventional triple immunosuppression: steroids, tacrolimus (prolonged-release –Advagraf, or immediate-release –generic or Prograf, according to their availability in each Spanish Community) plus mycophenolate mofetil (MMF) or mycophenolic acid (MPA).

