### **Appearance of donor-specific anti-HLA antibodies (DSA) and acute rejection.**

Steroid withdrawal at the third month post-transplant did not result in the appearance of DSA in patients with a low immunological risk, at least during the first two years of follow-up and using a MFI >500. No significant differences were found in the number of patients who experienced acute rejection after randomization between Group A (7.14%) and Group B (11.54%).

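### The primary DSA comparison has no planned effect estimate or confidence interval, so the reported absence of a DSA effect of steroid withdrawal goes further than the plan supports

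*Combined protocol and SAP*

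**What the plan says.** The Hypothesis section accepts that withdrawal can improve the metabolic and cardiovascular profile, then gives the open question: "it is not really known whether this therapeutic strategy results in a greater risk for the de novo appearance of donor-specific antibodies". It links such antibodies to reduced kidney graft survival. The Primary objective is neutral in wording: "To compare the incidence of de novo DSA in stable kidney transplant patients after withdrawal of steroids in the third month post-transplant", against continued triple therapy. Under Efficacy variables, the primary variable "was the presence of donor-specific anti-HLA antibodies (DSA) at 24 months".

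The Statistical Analysis Plan labels no analysis as primary. Three of its methods touch DSA:

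- the test for categorical variables: "The categorical variables were analyzed using the chi-square test or Fisher's exact test, according to needs";
- a longitudinal model: "Changes over time in the DSA and lymphocyte subsets in the two study groups were analyzed using a general linear model for repeated measures", adjusted for confounders;
- a risk-factor model: "a linear regression analysis was done to determine the factors associated with the generation of de novo DSA, including steroid withdrawal".

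None of the three has a stated effect measure, confidence interval or bound. The documents give no alpha, sidedness, margin, power or sample-size basis. The Blood pressure results call p=0.055 significant, so even 0.05 cannot be taken as certain.

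The Preliminary Results then state: "Steroid withdrawal at the third month post-transplant did not result in the appearance of DSA in patients with a low immunological risk". That sentence is limited to two years of follow-up and the MFI threshold of 500. It comes without counts, numbers tested, a difference or an interval.

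**The concern.** The clinical question is one of harm. A reader who wants to use withdrawal for its metabolic benefit needs to know how large an excess of DSA the trial rules out. A test of equal proportions does not answer that. It tends to be non-significant both when there is no excess and, at this size, when there is a moderate one. The smaller the number tested, the easier it is to obtain the reassuring result. Without an interval, a moderate rise in an antibody that the protocol ties to graft loss could be read as no effect.

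**Working it through.** **Inputs.** From the documents: 52 patients randomised to Group A and 53 to Group B; a binary primary variable; chi-square or Fisher. Assumed, because the documents are silent: control DSA rates of 2%, 5% and 10%; two-sided alpha 0.05; every randomised patient tested at month 24.

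**Step 1. A figure to reproduce.** There is no design figure. The Safety assessment p-values do show how binary outcomes were compared. Two-sided Fisher on the implied counts gives 0.110 for infections (5/52 vs 12/53; stated 0.110), 0.678 for cardiovascular events (3/52 vs 2/53; stated 0.677) and 0.618 for neoplasm (2/52 vs 1/53; stated 0.618). These were two-sided tests of no difference.

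**Step 2. How often the listed test is non-significant.** All outcome pairs were enumerated:

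P(non-significant) = Σ over a, b of Bin(a; 52, pA) × Bin(b; 53, pB) × 1[p(a,b) > 0.05], with pB = pA + excess.

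| Control rate | Test | +5 points | +10 points | +15 points |
|---|---|---|---|---|
| 2% | Fisher | 93.0% | 64.8% | 32.3% |
| 5% | Fisher | 92.6% | 72.5% | 44.5% |
| 10% | Fisher | 92.9% | 77.7% | 54.4% |
| 2% | Chi-square, uncorrected | 78.6% | 45.4% | 18.6% |
| 5% | Chi-square, uncorrected | 84.2% | 58.3% | 31.9% |
| 10% | Chi-square, uncorrected | 87.8% | 70.2% | 47.0% |

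A 5-point excess is nearly always missed and a 10-point excess usually is. A 15-point excess is found about as often as not, or more often.

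**Step 3. What an interval would add.** The Newcombe upper limit is d + √[(uB − pB)² + (pA − lA)²], where d = pB − pA and l, u are Wilson limits.

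- Zero events in both arms: lA = pA = pB = d = 0, so the limit equals uB = z²/(n + z²) = 3.841/(53 + 3.841) = 6.8 points. The Clopper-Pearson bound for 0/53 is close: 1 − 0.025^(1/53) = 6.7%.
- Illustrative 3/52 vs 6/53: d = 11.3 − 5.8 = 5.6 points (from unrounded rates), 95% CI −6.0 to 17.4, Fisher p=0.49. The p-value alone hides the 17.4.

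**Step 4. Fewer tested.** The rejection percentages after randomisation (7.14% and 11.54%) do not fit denominators of 52 and 53: 7.14% fits 3/42 or 2/28, and 11.54% fits 6/52 or 3/26. These are not DSA denominators, so 28 and 26 serve only as a low scenario. Zero events there would give 3.841/(26 + 3.841) = 12.9 points, and Fisher would miss a 10-point excess in 76–85% of trials.

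**The case against.** **The trial never claims non-inferiority.** This stands. The Primary objective only compares, and a reader might infer a non-inferiority trial that forgot its margin. The documents do not support that. But even a neutral comparison needs an effect estimate with its precision, and the stated conclusion needs a bound.

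**Chi-square or Fisher is not the only DSA analysis.** This also stands. The regression includes steroid withdrawal as a factor. It would be wrong to call the categorical test the only planned primary analysis. It is the only listed between-arm method that fits a binary variable by type, and the other two have no stated interval or bound.

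**The DSA statement might describe zero events, not a non-significant test.** It gives no p-value, whereas the next sentence, on rejection, speaks of significance. A reader might infer that the conclusion was drawn from a failed test; the text does not show that. If there were no events among 53, a large excess is implausible: a true Group B rate of 12% gives 0/53 with probability 0.88^53 = 0.1%, and 15% gives 0.85^53 = 0.02%. The miss rates in Step 2 would then describe the plan and not these data. The interval still matters, because it tells the reader that about 6.8 points remain open.

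**Missing samples.** A reader might also infer that lost month-24 samples produced the result. No section reports missing DSA samples, so that is not claimed here.

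**Conclusion.** The concern holds in a limited form. The plan specifies nothing that bounds the excess DSA risk of withdrawal, and the results sentence reads as if it did. Under the stated assumptions, Fisher is non-significant in about 93% of trials for a true 5-point excess, 65–78% for 10 points and 32–54% for 15 points. On the zero-event reading the unexcluded excess is about 6.8 points if all were tested, and more if fewer were. The miss rates depend on assumed DSA rates and alpha; the zero-event bound depends only on the numbers tested and the interval method. Nothing here suggests that withdrawal does raise DSA. The fault lies in how the comparison is planned and worded, and the data already held can repair it.

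**What to change.** In the Statistical Analysis Plan, add for the primary variable: *DSA counts and numbers tested by arm, and the risk difference (Group B minus Group A) with a two-sided 95% confidence interval, for both the intention-to-treat and the final-treatment sets.* Name one interval method, Newcombe or exact. Label the addition post hoc if it is made after outcome data were examined; the trial is open-label, so unblinding is not the relevant moment. Keep the chi-square or Fisher p-value as descriptive.

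Set no margin now. The documents contain none, and one chosen after the results would not be credible. A strict rule would also be hard to meet at this size: with an illustrative 10-point limit on the Newcombe upper bound and no true difference, 52 and 53 patients would pass in only 77%, 51% and 36% of trials at control rates of 2%, 5% and 10%.

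In the Preliminary Results, if the data bear it out, replace the DSA conclusion with: *no increase was detected; an excess of up to X points (upper 95% limit) is not excluded.*

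The cost is one interval per analysis set and a few sentences, with no new patients or procedures. The downside is a more guarded conclusion.
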